Brief Summary	Phthalates and bisphenols have been detected in a range of infant care products. This pilot study will test whether intervening on these sources of exposure during the critical period of minipuberty affects infants' body burden of phthalates and bisphenols. We will recruit 10 participants from the ongoing NYU Children's Health and Development Study (CHES) cohort study who are >=37 weeks gestation or <6 months postpartum, carrying a singleton fetus or with a singleton infant, and intending to breastfeed or breastfeeding. We will randomly assign them to use either conventional baby products or phthalate- and bisphenol-free baby products for the first or next three months of their children's lives. Toward the end of the intervention, we will collect maternal breast milk and infant urine, and assay samples for phthalate metabolite and bisphenol concentrations.
Phase	N/A
Objectives	Aim 1: To assess the feasibility of an intervention designed to reduce infant phthalate and bisphenol exposure Aim 2 (exploratory): To compare urinary phthalate and bisphenol exposure levels in the intervention and non-intervention groups, as well as between mothers and children in the control group.
Methodology	Open-label randomized controlled trial

Endpoint	Participants are enrolled until they have been using the assigned diapers for 3 months, toward the end of which time we will collect maternal breast milk and maternal and infant urine to test for phthalate metabolite and bisphenol concentrations
Study Duration	1 year (allows for 6 months of data collection among 10 participants and 6 months of data analysis).
Participant Duration	3 months
Population	We will recruit 10 participants who are already enrolled in the NYU CHES study at the Brooklyn campus. Eligible participants will be ≥ 37 weeks gestation or < 6 months postpartum, carrying a singleton fetus or with a singleton infant, and intending to breastfeed or breastfeeding.
Study Site	NYULH-Brooklyn
Number of participants	10 participants
Description of Study Intervention/Procedure	Half of the participants will be randomly assigned to the intervention group and will receive a three-month supply of phthalate- and bisphenol-free baby products (e.g., wipes, diaper cream) and a subscription to a cloth diaper service.
Reference Therapy	Half of the participants will be randomly assigned to the control group and provided with a three-month supply of conventional disposable diapers (e.g., Huggies or Pampers) and baby products (e.g., wipes, diaper cream).
Key Procedures	Three-month adherence to diaper assignment and one-time infant urine collection and maternal breast milk collection.
Statistical Analysis	Our primary aim is to assess the feasibility of the intervention; the project is not adequately powered to detect statistically significant differences between groups. However, we will compare distributions of chemicals between the two infant groups to assess the effectiveness of the intervention and also between mothers and children from the control group to assess the relative prevalence of particular bisphenols or phthalates in diet (reflected in maternal breast milk concentrations) vs. baby products (reflected in infant urinary concentrations).

CONFIDENTIAL

Schematic of Study Design

Key Roles

[name], MPH (Principal Investigator)

Assistant Professor, Department of Pediatrics, NYU Grossman School of Medicine
[name]
[contact]
[contact]

[name] (Sub-Investigator)

Pediatrics, Environmental Medicine & Population Health, NYU Grossman School of Medicine
Director and PI of NYU CHES Study
[name]
[contact]
[contact]

[name], MS (Sub-investigator)

Research Scientist, Lab Manager, Department of Pediatrics, Division of Environmental Pediatrics, NYU Grossman School of Medicine
[name]
[contact]
[contact]
(Analyze phthalate and bisphenol levels in urine and breast milk)

[name] (Sub-Investigator)

Research Data Associate, Department of Pediatrics, Division of Environmental Pediatrics, NYU Grossman School of Medicine
[name]
[contact]
[contact]
(Recruitment, consenting, project management, and data collection)

[name] (Study Team Member)

Assistant Professor, Department of Pediatrics, NYU Grossman School of Medicine
[name]
[contact]
[contact]
(Assist in analysis of urine and breast milk)

CONFIDENTIAL

This material is the property of the NYU Langone Health. Do not disclose or use except as authorized in writing by the study sponsor
Behavioral Intervention Template Version: 18 July 2022

1 Introduction, Background Information and Scientific Rationale

1.1 Background Information and Relevant Literature

In keeping with David Barker's fetal programming hypothesis,¹ studies of associations of phthalates and bisphenols with child health outcomes have focused on *in utero* exposure. Results have been inconclusive, however,^{2,3} with inconsistencies commonly attributed to varying approaches to exposure assessment and other methodological issues. An alternative explanation that has not been explored is the possibility that pregnancy may not be the only—or even the primary—critical period for early-life endocrine disruption. Minipuberty, a brief window during the first six months of life when sex hormones surge in sync with gonadal cell proliferation, may be a particularly vulnerable period for dysregulation of the hypothalamic-pituitary-gonadal axis by endocrine-disrupting chemicals (EDCs).⁴ Because of their estrogenic and anti-androgenic properties, bisphenols and phthalates have the potential to adversely affect the development of reproductive tissue responsible for sex hormone production, with downstream consequences for child health in multiple domains.

While most conceptual models linking EDCs to reproductive health outcomes have focused on prenatal exposure, including Niels Skakkebaek's Testicular Dysgenesis Syndrome theory⁵ and Germaine Buck-Louis's companion Ovarian Dysgenesis Syndrome theory,⁶ gestation is not the only critical period in the development of reproductive endocrine glands. Testicular Leydig and ovarian granulosa cells undergo three phases of maturation, culminating in sexual maturity. The first is mid-pregnancy, when Leydig cells proliferate in the fetal testis⁷ and primordial follicles emerge in the fetal ovary.⁸ The second is during minipuberty, when Leydig cells undergo another burst of proliferation and differentiation, and granulosa cells also proliferate as part of the postnatal surge in folliculogenesis.⁹ Finally, both become fully activated in puberty. During minipuberty, reproductive hormone concentrations rise precipitously, peaking between two and three months postnatally,⁴ only to become quiescent after about six months of age until reactivated during puberty. Disruption of this intricate choreography by exposure to EDCs could have negative consequences for the development of a variety of tissues and organs that are regulated by sex hormones, including brain, bone, adipocytes, and gonads.

Little research has been done on potential causes and effects of endocrine disruption during minipuberty. The only study to date to examine associations between EDCs and sex hormones during minipuberty reported positive associations between urinary bisphenol A (BPA) and both estradiol and the estradiol:testosterone ratio in the first three months of life.¹⁰ These results are consistent with BPA's estrogenic profile; the study did not measure phthalates, which are more commonly anti-androgenic. Sex hormones in minipuberty, in turn, have been linked with child health outcomes. Nearly all of the research in this area has focused on neurodevelopment, demonstrating links between lower testosterone levels in male infants and compromised auditory processing and language development.¹¹⁻¹⁵ Sex hormones also affect metabolism. One small study that examined minipuberty sex hormone levels and adipose tissue development found that testosterone and luteinizing hormone were negatively associated with body mass index, and estradiol was positively associated with skinfold thicknesses in boys.¹⁶

This pilot intervention study will assess the magnitude of infants' exposure to bisphenols and phthalates through common infant care products. If research continues to show child health consequences of bisphenol and phthalate exposure during minipuberty, these products could eventually be targeted for regulation.

CONFIDENTIAL

1.2 Rationale

Infants are highly exposed to phthalates and bisphenols, ubiquitous EDCs that have both estrogenic and anti-androgenic activity. Phthalates and bisphenols have been detected in a range of infant care products, including diapers,^{17,18} wipes, baby lotions, soaps, shampoos,¹⁹ and plastic baby bottles.²⁰ Exposure is magnified by infants' high surface-to-volume ratio and by the increased efficiency of dermal absorption via the thin skin surrounding their enlarged genitalia.²¹ This pilot study will test whether intervening on these sources of exposure during the critical period of minipuberty affects infants' body burden of phthalates and bisphenols. If successful, this protocol may be scaled up and eventually evidence may be used to inform regulation of chemicals contained in infant care products and educational outreach programs to protect children's health.

Aim 1: To assess the feasibility of an intervention designed to reduce infant phthalate and bisphenol exposure.

H1: We will successfully recruit participants from within an existing cohort study and collect biosamples from participants and their children in a single follow-up study visit.

Aim 2 (exploratory): To compare urinary phthalate metabolites and bisphenols between the intervention and non-intervention groups, as well as between mothers and children in the control group.

H2: Chemical levels will be higher among infants in the control group vs. the intervention group. There will be no difference in average chemical concentrations between the two groups of mothers. Among controls, different chemicals will be present in breast milk vs. infant urine.

1.3 Potential Risks & Benefits

1.3.1 Known Potential Risks

There is no excess risk to participants in this study due to the intervention being tested, which is designed to reduce the risk of endocrine disruption. The phthalate- and bisphenol-containing disposable diapers and baby products that the control group will receive are by far the standard in the US. We hypothesize that the phthalate- and bisphenol-free diapers and baby products that the intervention group will receive will reduce their risk of health outcomes associated with EDC exposure.

There is a risk of loss of confidentiality or privacy in relation to personal information and specimens to be collected upon participation in this study. We will make every effort to protect participants' privacy by labeling their samples and information only with a code, and keeping the key to the code in a password-protected database accessible only to IRB-approved study personnel.

There is no excess risk to participants associated with completing questionnaires. Participants may feel frustrated from answering questions. If that happens, participants are free to skip any questions they do not wish to answer.

1.3.2 Known Potential Benefits

Participants may gain the knowledge that they will be contributing to research that may improve our understanding of the relation between baby products, EDC exposure, and minipuberty.

CONFIDENTIAL

2 Objectives and Purpose

2.1 Primary Objective

The primary objective of this study is to assess the feasibility of an intervention designed to reduce infant phthalate and bisphenol exposure during the potential critical period of minipuberty. Specifically, we aim to evaluate the feasibility of an intervention that targets EDC exposure through randomly assigning participants to receive conventional diapers and baby products or cloth diapers and phthalate- and bisphenol-free baby products from birth through age 3 months.

2.2 Secondary Objectives

The secondary and exploratory objective for this study is to compare urinary phthalate and bisphenol exposure levels in the intervention and non-intervention groups, as well as between mothers and children in the control group

3 Study Design and Endpoints

3.1 Description of Study Design

- This is a single-site pilot intervention study to be conducted at NYU Langone Health-Brooklyn.
- Participants will be recruited from the ongoing pregnancy/birth cohort study, NYU CHES study.
- Participants will be randomly assigned to an intervention group (N=5) or a control group (N=5).
- Participants will receive a 3-month supply of either disposable diapers and conventional baby products (control group) or cloth diapers and phthalate- and bisphenol-free baby products (intervention group) at no cost.
- Participants will complete brief adherence surveys at three postnatal time points.
- After 3 months, study personnel will conduct a study visit during which maternal breast milk and maternal and infant urine will be collected.
- Urine and breast milk samples will be analyzed for phthalate metabolites and bisphenols in the NYU Human and Environmental Exposure Assessment Facility Core lab.

3.2 Study Endpoints

3.2.1 Primary Study Endpoints

The primary endpoint, needed to fulfill Aim 1, is when the total number of participants (N=10) have used their assigned baby products for three months and the two biospecimens (maternal breast milk and infant urine) have been collected from all participants.

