4.4 Strategies for Recruitment and Retention

Potentially eligible participants will be identified by Diaper Study personnel from among those already enrolled in NYU CHES study at the Brooklyn campus. All Diaper Study personnel will be added to the NYU CHES study. Potential participants will be recruited either by phone or at an in-person prenatal visit at ≥37 weeks gestation or within 6 months postpartum.

- **Remote Screening**

- Potential participants will be contacted via phone using an IRB-approved telephone recruitment script. If they are interested in hearing more about the study, study staff will ask screening questions over the phone to confirm eligibility.
- If potential participants are eligible and still interested in learning more about the study, potential participants will be sent the REDCap link to the Key Information Sheet and Informed Consent and will be given the phone number of a study team member to call after they have reviewed the consent materials. Refer to Section 12.3.2 for more information on the consent procedures.
- If potential participants are not eligible and/or do not wish to take part in the study, their PHI (phone number, address, and any other PHI) will be discarded at this point.

- **In-Person Screening**

- If possible or preferred by the potential participant, screening may occur in person at the NYULH Brooklyn location. This will be coordinated by study staff.
- Study staff will give the potential participant a physical copy of the Key Information Sheet and Study Infographic if it has not already been sent to them. If the potential participant is interested, study staff will ask screening questions to confirm eligibility.
- If the potential participant is eligible and still interested in learning more about the study, the study staff member will walk the potential participant through Informed Consent. If the potential participant wishes to take part in this study, she will be asked to sign a paper copy of the Informed Consent. Refer to Section 12.3.2 for more information on the consent procedures.

In order to retain enrolled participants, we will visit them in the hospital following delivery or via phone call if a birth visit is not possible in order to inform participants of their group assignment and contact them again two weeks and six weeks after birth to check in on the diaper delivery logistics and assess and encourage group assignment adherence.

CONFIDENTIAL

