4.7.2 Handling of Participant Withdrawals or Termination

If a participant withdraws between the time of consent and biospecimen collection, the participant will be replaced.

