9.2 Statistical Hypotheses

Aim 1: H1: We will successfully recruit participants from within an existing cohort study and collect biosamples from participants and their children in a single follow-up study visit.

Aim 2: Chemical levels will be higher among infants in the control group vs. the intervention group. There will be no difference in average chemical concentrations between the two groups of mothers. Among controls, different chemicals will be present in breast milk vs. infant urine.

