9.4 Description of Statistical Methods

9.4.1 Analysis of the Primary Efficacy Endpoint

Our primary aim is to assess the feasibility of the intervention. There are no relevant statistical endpoints.

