9.4.4 Adherence and Retention Analyses

We will calculate the percent of participants that complete the study as well as the average adherence to protocol in each of the two arms based on participant self-report.

CONFIDENTIAL

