9.4.6 Enrollment/Randomization/Masking Procedures

Participants will be assigned to either the intervention or control group on an alternating basis upon enrollment. Because of the nature of the intervention (cloth vs. conventional diapers), they will not be blinded. If a participant needs to be replaced, the replacement will be assigned to the same group as the participant who withdrew.

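### The primary feasibility endpoint is a milestone that replacement can reach at very different attrition rates, and no denominator or recruitment measure is tied to it

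*Combined protocol and SAP*

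**What the plan says.** Section 2.1 makes feasibility the primary objective. Under section 3.2.1 the primary endpoint "is when the total number of participants (N=10) have used their assigned baby products for three months" and breast milk and infant urine have been obtained from everyone. No proportion, denominator or success criterion is given.

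On drop-out, section 4.7.2 says: "If a participant withdraws between the time of consent and biospecimen collection, the participant will be replaced". Section 9.4.6 adds that "the replacement will be assigned to the same group as the participant who withdrew". Neither section caps the number of replacements. Section 4.6 expects usable data from every pair, and section 9.4.5 says that the budget set the size at 5 per group.

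On analysis, section 9.4.1 says of the primary aim: "There are no relevant statistical endpoints". Section 9.4.4 states: "We will calculate the percent of participants that complete the study", together with average self-reported adherence in each arm. It does not say who is in the denominator once someone has been replaced.

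On recruitment, H1 in section 9.2 reads: "We will successfully recruit participants from within an existing cohort study and collect biosamples from participants and their children in a single follow-up study visit". No section plans a count of women approached, eligible or consented. For women screened remotely who are ineligible or decline, section 4.4 says that "their PHI (phone number, address, and any other PHI) will be discarded at this point".

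**The concern.** A feasibility pilot is run to learn how many women agree to take part, how many stay, and how many yield the specimens. A primary endpoint that is declared once ten pairs have finished, with withdrawals refilled, does not carry that information. A trial that lost several mothers and a trial that lost none would report the same primary result.

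The one percentage that could tell them apart, in 9.4.4, sits outside the primary endpoint, and its denominator is open. With the planned size fixed at 10, both 10/10 and 10/14 are permitted readings of the same trial. The recruitment half of H1 has no planned measure, so a reader could not tell whether ten consents came from twelve approaches or from a hundred. Anyone planning a larger trial needs these rates to set its recruitment period and over-enrollment.

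**Working it through.** **The plan's own figure.** 5 + 5 = 10 pairs, which agrees with sections 3.1 and 9.4.5. The number comes from the budget, so there is no power or precision calculation to reproduce.

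**Inputs.** Ten completers are needed (3.2.1). Withdrawals are replaced in the same arm without a stated cap (4.7.2, 9.4.6). The documents give no completion rate, so p, the true probability that an assigned pair completes, is assumed over 50% to 95%. Pairs are taken as independent, with the same p in both arms, and every non-completion is taken to be a withdrawal that is replaced.

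**Step 1: what replacement does.** Without replacement, the chance that all ten complete is p^10. With replacement, the number enrolled to obtain ten completers is negative binomial with mean 10/p (5/p per arm, summed over two arms).

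| Assumed p | p^10, no replacement | Mean enrolled, 10/p | 95th percentile enrolled | Endpoint in 3.2.1 |
|---|---|---|---|---|
| 95% | 0.60 | 10.5 | 12 | met |
| 80% | 0.11 | 12.5 | 16 | met |
| 70% | 0.03 | 14.3 | 19 | met |
| 50% | 0.001 | 20.0 | 28 | met |

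The last column assumes that enough recruits and time are available. Without replacement, the milestone would at least respond to attrition. With it, only the number enrolled responds, and that number is not part of the endpoint.

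**Step 2: what a full denominator would show.** Let x be the completers and n all assigned pairs. The exact (Clopper-Pearson) 95% limits are the 2.5% point of Beta(x, n - x + 1) and the 97.5% point of Beta(x + 1, n - x). For x = n = 10 the lower limit is 0.025^(1/10) = 0.692 and the upper limit is 1.

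| Completed / assigned | Proportion | Exact 95% CI |
|---|---|---|
| 10/10 | 100% | 69-100% |
| 10/12 | 83% | 52-98% |
| 10/14 | 71% | 42-92% |
| 10/20 | 50% | 27-73% |

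All four rows satisfy 3.2.1 equally. By arm the precision is lower still: 5/5 has an interval of 48-100%. Enrolling until ten complete departs slightly from fixed-n binomial sampling, but the effect is small: for 10/14 the upper limit becomes 0.909 instead of 0.916.

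**Step 3: recruitment.** H1 claims successful recruitment. The natural measure is consented divided by eligible and approached. Neither number is planned anywhere in the protocol.

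**The case against.** The strongest reply is that the protocol does plan feasibility data. Section 9.4.4 gives percent completing and adherence by arm, section 6.1.1 collects adherence three times, and section 8 places drop-out rates under the monitoring plan. A reader might infer that the trial cannot show feasibility at all, or that it will report 10 of 10 whatever happens. The documents support neither inference. Retention and adherence evidence will exist, and nothing says that replaced mothers leave the 9.4.4 denominator. What stands is that the denominator is unstated and the percentage is not the primary endpoint.

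Other stronger readings also fail:

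- **The endpoint is certain to be met.** Section 4.7.2 speaks of a participant who withdraws. It does not say that mothers lost to follow-up or terminated by the investigator are replaced. The Protocol Summary allows 6 months of data collection, and each replacement needs her own 2 to 3 months of use (6.3.5). Heavy attrition could therefore leave the milestone unmet, although 3.2.1 does not make that period a failure criterion.
- **One failed urine bag sinks the endpoint.** If each pair had a 90% chance of yielding both specimens, all ten would fail to deliver with probability 1 - 0.9^10 = 65% (at 80%, 1 - 0.8^10 = 89%). Those yields are assumed, and nothing bars a second attempt. With one independent retry the figures are 1 - 0.99^10 = 10% and 1 - 0.96^10 = 34%. They cannot serve as the size of the problem.
- **Screening records are destroyed.** Section 4.4 discards identifying information, in the remote-screening bullets only. Anonymous counts are not prohibited, and candidates come from the cohort database. The valid point is that no tally is planned.
- **A feasibility result triggers the next trial.** The remark in section 1.2, "If successful, this protocol may be scaled up", follows a sentence about infants' body burden and states no decision rule.

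It is also fair to say that a numerical threshold is a matter of choice in a ten-pair, budget-limited pilot. The intervals for 10/12 and 10/14 overlap almost entirely, so an 80% cutoff would not separate them reliably.

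**Conclusion.** The concern holds for the primary endpoint as defined, not for the trial as a whole. Section 3.2.1 sets a milestone that replacement allows to be reached at very different attrition rates. No analysis is attached to it, the related percentage in 9.4.4 is unlinked and has an open denominator, and the recruitment part of H1 has no measure.

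As an illustration of size, true completion of 95%, 80% and 70% leads to the same primary result after 10.5, 12.5 and 14.3 pairs on average, while the proportion of all assigned pairs could be 100%, 83% or 71%. This rests on assumed completion rates, independent pairs, replacement of every non-completer, and enough time and recruits. The structural point depends on none of the particular rates, but it does need replacement to be achievable in practice.

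**What to change.** - In 3.2.1, 9.4.1 and 9.4.4, define the primary feasibility measure as the proportion of all assigned mother-infant pairs who provide both breast milk and infant urine and report using the assigned products. Pairs who withdraw or are replaced stay in the denominator as not completed. Section 9.4.6 assigns at enrollment, so this denominator is known.
- Report the proportion overall and by arm with exact 95% confidence intervals.
- Add a recruitment proportion, consented divided by eligible and approached, from a count-only, de-identified screening log kept for remote and in-person screening when identifying information is discarded.
- A success threshold is optional. If the sponsor wants one, it should be set in advance.

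The cost is protocol wording, a simple tally and a few binomial intervals, with no added participants, visits or assays. The tally should be in place before enrollment, because the counts may not be recoverable later. The downside is that the reported completion rate may be less favorable and the intervals will be wide at this size.
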